## 3 DATA ANALYSIS CONSIDERATIONS

### 3.1 Timing of Analyses

Participant data will be locked prior to the final analysis of each Substudy, and outputs will be produced and reported in a CSR. Participants who have completed study may have their data frozen once their data is clean. Further details are provided under each study subsection.

Data will be hard locked once all Substudies are completed, and data will be presented per Substudy (and part if applicable) within a CSR, using the Data cut-off (DCO) of the primary analysis within each Substudy. Analyses already completed within previous Substudies will not be re-run at the hard lock. Additional information on how the data will be presented for each Substudy is provided in the corresponding sections of the SAP.

The final analysis of the study is planned 18 months after the last enrolled participant received his/her first dose of study IP or when the Sponsor stops the study, whichever occurs first. End of study will be based on the last Substudy open.

Further details on the analyses planned are provided in [Table 1](#).

#### 3.1.1 Substudy 1

For Substudy 1, data is presented separately for part A, B and C. For part A data is presented by dose level and overall. For part B, data is presented in separate tables by tumour type, by dose level and overall. For part C, data is presented in separate tables for indication by dose level (as applicable at the time). No direct statistical comparisons will be made between any cohorts or expansions.

One interim analysis is planned for Part C in this Substudy. Recruitment will not be paused while the participants required for the interim analysis are being evaluated.

At the completion of each part within Substudy 1, a primary analysis will be conducted (analysis will be conducted separately for each part).

**Table 1: Timing of analysis**

Analysis	Trigger	Data Type Included
Final analysis	The end of the study is defined as 18 months after the last enrolled participant received his/her first dose of study IP or when the Sponsor stops the study, whichever occurs first.	All data*
Substudy 1		
Interim for efficacy expansions (Parts C1 and C2)	After the 20 th participant in each expansion had the opportunity for 2 on-treatment RECIST assessments	Efficacy (RECIST v1.1 ORR, DoR, DCR at 15 weeks, PFS, OS and tumour size)  Safety
Primary analysis	At completion of each part (primary analysis is conducted separately for each part):	All appropriate data

DCR = disease control rate; DoR = duration of response; IP = Investigational Product; ORR = objective response rate; OS= Overall Survival; RECIST = Response Evaluation Criteria in Solid Tumours v1.1; PFS = Progression Free Survival.

\*Data will be presented by part at the final analysis of the Substudy, except for safety analyses, which will be presented by part and for Part A + Part B if same patients and same dose (See section [4.2](#)).

## 3.2 Analysis Populations

All participants who receive any amount of IP are included in the Safety analysis set. For the safety and PK analyses, participants are classified according to the IP starting dose. For all efficacy analyses, and for baseline and demography, participants are classified according to the dose they were assigned to (i.e., the planned IP dose level).

The following populations are defined in [Table 2](#).

**Table 2: Populations for Analysis**

Population/Analysis set	Description	Endpoint/Output
Enrolled	All participants who sign the ICF	Disposition
Safety	All participants who receive any amount of IP.	Baseline and demographics Exposure Safety endpoints PK concentrations listings

Population/Analysis set	Description	Endpoint/Output
		PK parameters listings Immunogenicity listings PFS OS ctDNA
DLT Evaluable	Enrolled participants who complete the DLT evaluation period (defined as 21 days after receiving the first infusion of IP) with at least 75% dosing* and have completed safety evaluation requirements during the DLT evaluation period, as defined in the CSP  OR  Patients who experience any DLT during the DLT evaluation period.	DLT
Response Evaluable	All dosed participants who have measurable disease at baseline.	ORR DoR BoR DCR at 15 weeks Percentage change in tumour size
Pharmacokinetics	All participants who receive at least one dose of IP with at least one reportable concentration. **	PK concentrations PK parameters
Immunogenicity	All participants who receive at least one dose of IP who have a non-missing baseline ADA result and at least 1 non-missing post-baseline ADA result	Incidence of ADA ADA titer
Substudy 1 Population		
Interim Response Evaluable (Interim – Expansion only)	All dosed participants who had measurable disease at baseline and have had the opportunity for 2 on-treatment RECIST assessments (16 weeks, 6+9 weeks + 1 week window) or have had 2 on schedule tumour assessments.	ORR at interim DoR BoR at interim Tumour size
Pharmacodynamics	All participants who receive at least one dose of IP with baseline measurement and at least one	Change in circulating GDF15 serum levels (applicable for Part A and Part B only).

Population/Analysis set	Description	Endpoint/Output
	reportable pharmacodynamic measurement.	Change in CD8 tumour infiltration by IHC using baseline and on treatment samples (applicable to Part B only).

ADA=Anti-Drug Antibody; BoR=Best Overall Response; CD8=cluster of differentiation 8; ctDNA=circulating tumour deoxyribonucleic acid; DCR=disease control rate; DLT=dose limiting toxicity; DoR=duration of response; FAS = Full analysis set; ICF= informed consent form; IP= Investigational product; ITT=Intention to treat; PET=positron emission tomography; PFS=Progression Free Survival; PK=pharmacokinetics; PD=pharmacodynamics; OS= overall survival; ORR= objective response rate; RECIST = Response Evaluation Criteria in Solid Tumours v1.1.

\*Please refer to section 4.2.1.1 for the derivation of percentage of dosing.

\*\* Individual PK concentration and parameter data for any participants who are excluded from the descriptive summary tables, figures and/or inferential statistical analyses are included in the listings and are flagged with an appropriate footnote.

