#### **4.2.4.2 Derivations**

A programmed derivation for DCR is:

- If participants have a BOR of confirmed CR or PR, they have disease control.

- Or if a participant has SD to at least DCR time point (i.e., duration of SD  $\geq$  DCR time point), they have disease control. (Note participants with unconfirmed responses should be included in this calculation.)
  - Duration of SD is defined as the time from first IP dose until the first documentation of disease progression or death due to any cause, whichever occurs first:
    - Duration of SD (days) = Disease progression or death or PFS censoring date – first IP dose date +1. SD after the start of subsequent cancer therapy should not be included in this duration.
- Otherwise, they do not have disease control.

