## 5 INTERIM ANALYSIS

### Substudy 1

In the efficacy expansions (Part C1 and Part C2) an interim analysis is performed after the 20th participant in each expansion has had the opportunity for 2 on-treatment RECIST v1.1 assessments or has discontinued or withdrawn from treatment. Enrolment will continue while this analysis is ongoing. The analysis will provide tolerability and safety data and will also provide a reasonable chance to determine if there is a lack of efficacy. CCI

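### DCR at 15 weeks is a Part C interim output, but SAP Table 2 leaves it out of the follow-up-restricted interim set; read literally, interim DCR is biased downward

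*SAP*

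**What the plan says.** **Interim outputs.** SAP Table 1 lists for the Part C1 and C2 interim: "Efficacy (RECIST v1.1 ORR, DoR, DCR at 15 weeks, PFS, OS and tumour size". The trigger is that the 20th "participant in each expansion had the opportunity for 2 on-treatment RECIST assessments".

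**Populations.** SAP Table 2 has two response sets.
- Response Evaluable is "All dosed participants who have measurable disease at baseline". Its endpoints are "ORR DoR BoR DCR at 15 weeks Percentage change in tumour size".
- Interim Response Evaluable adds a follow-up condition: the opportunity for two on-treatment scans ("16 weeks, 6+9 weeks + 1 week window) or have had 2 on schedule tumour assessments"). Its endpoints are "ORR at interim DoR BoR at interim Tumour size". DCR is not among them.

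**DCR rule.** Under SAP 4.2.4.1 and 4.2.4.2, disease control needs either a confirmed CR or PR, or SD lasting at least 14 weeks from first dose. For everyone else: "Otherwise, they do not have disease control". SD duration runs to progression, death or the PFS censoring date. Table 9 puts that censoring date, for a participant still progression-free, at the last evaluable disease assessment.

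**Recruitment.** SAP 3.1.1 keeps recruitment open while the participants needed for the interim are being evaluated.

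**The concern.** The SAP protects interim ORR, BOR, DoR and tumour size from immature follow-up by giving them a restricted set. DCR is reported at the same interim without that protection. It arguably needs it most, because its SD component cannot be met before 14 weeks.

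The derivation has no category for a participant who is not yet assessable. A programmer who follows Tables 1 and 2 literally would compute interim ORR on mature participants and interim DCR on everyone dosed, in the same report. The error can only lower DCR. Section 5 says the interim should help detect a lack of efficacy, so a DCR that is low for reasons of timing could mislead whoever reads it.

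**Working it through.** **1. The plan's own figure.** The interim set's window is 6 + 9 + 1 = 16 weeks, as Table 2 states. No interim DCR or operating characteristic is visible, so there is none to reproduce.

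**2. Can a recently dosed participant qualify through SD?**
- Threshold: 14 × 7 = 98 days.
- Study Week 6 scan window: days 5 × 7 + 1 = 36 to 42. With only that scan, SD duration is 36 to 42 days, below 98.
- Study Week 15 Day 1: 14 × 7 + 1 = day 99, giving a duration of 99 days, which meets the threshold.

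Until the Week 15 scan is done, the only route to disease control is a confirmed response. That means a response at Week 6 and a repeat scan at least 4 weeks later, before the next scheduled scan 9 weeks on. It is possible but should be uncommon.

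**3. Effect on interim DCR.** Inputs: 20 mature participants (the trigger in Table 1); true DCR *p* and number of immature participants *m* (both assumed, neither is in the documents). With a planned expansion of 40, *m* is at most 40 − 20 = 20. If none of the *m* has a confirmed response:

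Expected interim DCR = 20*p* / (20 + *m*)

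| True DCR | m = 0 | m = 5 | m = 10 | m = 20 |
|---|---|---|---|---|
| 20% | 4/20 = 20.0% | 4/25 = 16.0% | 4/30 = 13.3% | 4/40 = 10.0% |
| 30% | 6/20 = 30.0% | 6/25 = 24.0% | 6/30 = 20.0% | 6/40 = 15.0% |
| 40% | 8/20 = 40.0% | 8/25 = 32.0% | 8/30 = 26.7% | 8/40 = 20.0% |
| 50% | 10/20 = 50.0% | 10/25 = 40.0% | 10/30 = 33.3% | 10/40 = 25.0% |

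For the 40% row, the planned two-sided 90% Clopper-Pearson intervals are 21.7–60.6%, 17.0–50.4%, 14.0–43.0% and 10.4–33.2%.

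**4. What accrual gives these values of m?** Anyone first dosed in the last 14 weeks before the cut cannot yet qualify through SD. With 365.25/12 = 30.44 days per month, 14 weeks is 98/30.44 = 3.22 months. So *m* = 5, 10 and 20 correspond to 5/3.22 = 1.6, 10/3.22 = 3.1 and 20/3.22 = 6.2 participants per month per expansion.

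**5. Allowing for early confirmed responses.** With *p* = 40% and *m* = 10, if 5% or 10% of the later participants already had one, the result is (8 + 0.5)/30 = 28.3% or (8 + 1)/30 = 30.0%. It is still below 40%.

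**The case against.** The strongest reply is that DCR was probably left off the interim row by oversight, and that a sensible programmer would use the interim set anyway. That may be what the sponsor intends. It does not settle the matter, because the only row of Table 2 that names DCR is the unrestricted one.

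A reader might also infer more than the documents support:
- **That section 4.2.4.3 fixes the full set as the interim population.** It assigns only the main analysis of DCR to Response Evaluable. ORR and BOR are worded the same way in 4.2.2.4 and 4.2.3.4, yet both have an interim set. The case rests on Tables 1 and 2.
- **That DCR drives a futility decision.** No visible rule uses it. The text after the interim paragraph in section 5 is redacted, and the stated sizing rationale for Part C is precision of ORR.
- **That a faster-enrolling expansion would be judged worse than the other.** The SAP plans no direct statistical comparison between expansions. The distortion does differ with accrual, but it stays within each expansion's own figure.
- **That continued enrolment during the analysis is the cause.** The sentence "Enrolment will continue while this analysis is ongoing" concerns the period of the analysis itself, and participants dosed after the data cut-off are not in it. The relevant statement is in 3.1.1, about recruitment while the first 20 mature.

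The interim also gives ORR on the mature set and Kaplan-Meier PFS, which censors immature participants, so DCR is not read alone. These points limit the consequence. They do not remove the conflict between the tables.

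**Conclusion.** The point holds as a conflict between SAP Tables 1 and 2 which, if the tables are followed literally, biases interim DCR downward and gives it a different denominator from interim ORR. Nearly all participants without a Week 15 scan would count as failures; those with an already confirmed response would not.

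The attenuation factor is 20/(20 + *m*): 0.80, 0.67 and 0.50 for 5, 10 and 20 later participants. It is exactly 1 only if no one is dosed after the 20th. These sizes rest on assumed accrual and an assumed true DCR, and illustrate one reading of the tables rather than a property of the plan. DCR at full maturity is unaffected. This should be corrected before the interim data cut-off, but it does not threaten the trial's final conclusions.

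**What to change.** In SAP Table 2, add DCR at 15 weeks at interim to the endpoints of the Interim Response Evaluable row. In section 4.2.4.3, add one sentence saying that interim DCR uses that set, with the same denominator as interim ORR.

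The cost is two short wording changes and a smaller interim DCR denominator (about 20 rather than all dosed), with no new data and no design change.

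Two things should be left alone. A separate 15-week denominator rule for DCR would not match the interim set's condition of 16 weeks or two on-schedule assessments, and so would again separate DCR from ORR. The Response Evaluable population for the part-level primary analysis should stay as the protocol defines it.

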10.9.5 Interim Analyses

In the efficacy expansions (Part C1 and Part C2) an interim analysis will be performed after the 20th participant in each expansion has had the opportunity for 2 on-treatment RECIST assessments or has discontinued or withdrawn from treatment. Enrolment will continue while this analysis is ongoing. The analysis will provide tolerability and safety data and will also provide a reasonable chance to determine if there is a lack of efficacy.

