Version 3.0	28/06/2023	
The RECIST timepoints are incorrectly defined in the SAP, the study weeks does not equal the time following first IP, for example, the first RECIST assessment is expected at study week 6, which is 5 weeks following first IP rather than 6 weeks following first IP which was incorrectly being used in the SAP.
 

• Section 4.2.3.2 - Best Overall Response Derivation:

○ Updated the derivation for patients who dies with no evaluable RECIST assessments. The current definition incorrectly defines the first assessment timepoint at 6 weeks after 1st IP dose instead of 5 weeks

○ Updated the derivation for stable disease. The current definition incorrectly defines the first assessment timepoint at 6 weeks after 1st IP dose instead of 5 weeks.

• Section 4.2.4 – Disease control at Study week 15:

○ Disease control rate updated to be at study week 15 (14 weeks after first IP),, rather than at 15 weeks.

• Section 4.2.6.2 – Progression Free Survival Derivation:

○ Updated the definition of two missing consecutive visits, based on the correct RECIST timepoints.

• Section 4.2.7.2 – Change in Target Lesion Tumour Size Derivation:

• Clarified it is Study week 15, rather than week 15 throughout.

	All changes are in line with the CSP.	Correction of RECIST time windowing as per protocol.
-------------	------------	--	---------------------------------------	--

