#### **4.2.3.2 Derivations**

For participants who die with no evaluable RECIST v1.1 assessments, if the death occurs  $\leq$  15 weeks (i.e. 14 weeks [5 weeks + 9 weeks] + 1 week to allow for a late assessment within the assessment window) after first dose of IP, then BOR is assigned to the progressive disease

category. For participants who die with no evaluable RECIST v1.1 assessments, if the death occurs > 15 weeks after first dose then BOR is assigned to the NE category.

For CR/PR, the initial overall visit assessment that showed a response uses the latest of the dates contributing towards a particular overall visit assessment. A participant is classified as a responder if the RECIST v1.1 criteria for a CR or PR are satisfied at any time following first IP dose, prior to RECIST v1.1 progression and prior to starting any subsequent cancer therapy. CR or PR must be confirmed (see detail in Objective Response Section [4.2.2.1](#)).

For determination of a best response of SD, the earliest of the dates contributing towards a particular overall visit assessment is used. SD should be recorded at least 5 weeks (5 x 7 = 35 days) from first dose.

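### The Interim Response Evaluable set does not match the interim trigger and keeps a superseded 16-week figure; the resulting bias in interim ORR is small, but the look may run on well under 20 evaluable participants

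*SAP*

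**What the plan says.** Four places bear on the interim look in Parts C1 and C2.

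- **Trigger, SAP Section 5:** the look follows once the 20th participant in each expansion "has had the opportunity for 2 on-treatment RECIST v1.1 assessments or has discontinued or withdrawn from treatment". Protocol 10.9.5 has the same condition ("has had the opportunity for 2 on-treatment RECIST assessments or has discontinued or withdrawn from treatment"), and so does Protocol Table 22.
- **Trigger, SAP Table 1:** after the 20th "participant in each expansion had the opportunity for 2 on-treatment RECIST assessments". The clause on stopping treatment is absent.
- **Analysis set, SAP Table 2:** dosed participants with measurable disease who have had time for two on-treatment assessments, or who already have two: "16 weeks, 6+9 weeks + 1 week window) or have had 2 on schedule tumour assessments". Nothing admits a participant because they stopped. Interim ORR, BOR, DoR and tumour size use this set.
- **Timing elsewhere in the SAP:** Section 4.2.3.2 (BOR) now uses "14 weeks [5 weeks + 9 weeks] + 1 week to allow for a late assessment", that is 15 weeks, and Section 4.2.6.2 (PFS) also uses 14 weeks plus 1. The v3.0 entry in the Amendment History gives the reason: "the first RECIST assessment is expected at study week 6, which is 5 weeks following first IP rather than 6 weeks following first IP". Its list of corrected sections does not include Section 3.2, where Table 2 sits.

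For the main ORR analysis, SAP Section 4.2.2.4 keeps participants with no assessments in the denominator as non-responders.

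**The concern.** The rule that decides when to look and the rule that decides who is analysed treat early stoppers differently. A participant who progresses at the first scan counts toward the trigger in Section 5, yet can be missing from the interim ORR denominator if dosed recently enough. A participant dosed on the same day who continued to a second scan is included. One stated purpose of the look is to detect lack of efficacy. Dropping early failures raises the observed ORR, and a smaller denominator raises the upper confidence limit, so both work against that purpose. A literal reading of the trigger, under which only the 20th participant has to qualify, also allows the look to occur while others among the 20 are still short of their second scan.

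**Working it through.** **1. The plan's own figure.** Table 2: 6 + 9 + 1 = 16 weeks (112 days), which reproduces. With the first assessment 5 weeks after first dose, as in SAP v3.0: 5 + 9 + 1 = 15 weeks (105 days). The difference is 7 days.

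**2. Scan windows.** SAP Section 4.2.7.2 places the first two scans in study weeks 6 and 15, days 1 to 7, with no early allowance. Study week w covers study days 7(w−1)+1 to 7w, so the windows are days 36–42 and 99–105. Fifteen weeks is the close of the second window; 16 weeks is a week later.

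**3. Who is treated unequally.** Take opportunity to mean calendar time since first dose.

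| Time from first dose at cut-off | Two on-schedule scans done | Progressed, died or withdrew before second scan |
|---|---|---|
| Under 14 weeks | not yet possible: out | out |
| About 14 to 16 weeks | in | out |
| 16 weeks or more | in | in |

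The set's rule separates participants by outcome only in the middle row. Changing 16 to 15 would narrow that row to about one week but would not remove it. If the look waits for all 20, anyone still under 14 weeks can only be an early stopper; the simulated figures below include them.

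**4. Size of the ORR shift.** The documents give no drop-out or accrual rates, so these are assumptions: true ORR 15%; 45% of non-responders off by the first scan and 25% at the second; exponential enrolment gaps; second scan on days 99–105; inclusion at 112 days or two scans; 20,000 simulated interims per scenario; no Part B carry-over.

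| Reading of trigger | Enrolled per month | Mean retained of 20 | Mean interim ORR |
|---|---|---|---|
| All 20 must qualify | 2 to 8 | about 19 | 15.7% to 16.0% |
| 20th participant only | 2 | 17.7 | 15.6% (low end) |
| 20th participant only | 4 | 15.7 | between |
| 20th participant only | 8 | 12.8 | 17.1% (high end) |

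The shift is 0.7 to 1.0 points on the first reading and 0.6 to 2.1 on the second. Only accrual was varied; heavier early drop-out would enlarge it.

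**5. Where the lost participants go on the literal reading.** At 2, 4 and 8 per month, 1.9, 3.4 and 6.2 of the 20 are under 14 weeks from first dose. Early failures lost in the 14-to-16-week band number 0.3, 0.6 and 0.7 to 0.9. At 8 per month, 20 − 12.8 = 7.2 are lost, and 6.2/7.2 = 86% of that is short follow-up.

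**6. What a smaller denominator does.** Two-sided 90% Clopper–Pearson, the SAP's method. With no responders the upper limit is 1 − 0.05^(1/n): 13.9% at n = 20, 17.1% at 16, 19.3% at 14. With 2 responders: 2/20 = 10.0% (1.8 to 28.3) and 2/16 = 12.5% (2.3 to 34.4).

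**The case against.** A timing trigger and an analysis set need not share wording: one says when to look, the other who has enough follow-up. That is fair, and a follow-up-based denominator is legitimate. It does not explain a two-scan limb that lets continuing participants in before 16 weeks while early failures wait.

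A reader might infer that everyone who fails early and is under 16 weeks is dropped while their continuing peers are kept. The scan windows do not support this: before study day 99 nobody can have two on-schedule scans. Nor is stopping treatment enough by itself, because Protocol 7.1 requires scans to continue until progression and the second limb of the set does not say on-treatment. The participants affected are those who progress, die or withdraw before the second scan.

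A reader might also take 12.8 of 20 as a count of discarded failures. Step 5 shows that it is mostly immaturity. The literal trigger is also the less natural reading, since Protocol 10.6.7 speaks of an interim after 20 participants. Up to 10 Part B participants may count toward each expansion and would probably be mature by then. With 10 assumed mature, the 8-per-month case becomes about 15.4 retained with ORR near 16%.

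Finally, early failures are not hidden. Table 1 lists PFS, OS and safety at the interim, and Table 2 puts these on all dosed participants. DCR is assigned to the full Response Evaluable set. All of this stands and limits the size of the point, but it does not reconcile the three SAP passages.

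**Conclusion.** The inconsistency is real. Table 1, Table 2 and Section 5 describe the interim in three different ways, and the 16 weeks in Table 2 conflicts with the 15 weeks used for the same two assessments elsewhere in the current SAP. Inclusion depends on outcome in a band of about two weeks. The upward bias in interim ORR is small: roughly 1 point or less if the look waits for all 20, and up to about 2 points on a literal 20th-participant trigger with fast accrual. For scale, 3/20 has a 90% interval of 4.2% to 34.4%. The larger consequence of the literal reading is a look on well under 20 evaluable participants, mainly through short follow-up. These sizes rest on assumed response, drop-out and accrual rates and ignore Part B carry-over.

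A reader might conclude that the lack-of-efficacy decision is compromised. The documents cannot show that: text directly after the purpose statement in Section 5 is redacted, so the effect on go/no-go cannot be computed. The change should be made because the text contradicts itself and is cheap to repair, not because a large bias has been demonstrated.

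**What to change.** Use one definition in SAP Table 1, Table 2 and Section 5:

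- **Set:** the first 20 dosed participants per expansion with measurable disease, including any counted from Part B.
- **Trigger:** when every one of those 20 is at least 15 weeks from first dose, or has progressed, discontinued, withdrawn or died.
- **Denominator:** all 20, as non-responders unless a confirmed response is recorded, in line with Section 4.2.2.4.

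Inclusion then cannot depend on outcome and the denominator is known in advance. In the same edit, correct the first-scan timing in SAP Appendix A (Section 7.1), which still places it 6 weeks after first dose.

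The cost is SAP wording only. The look may come a few weeks later than under a literal 20th-participant trigger; enrolment already continues during it.
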